4. ANALYSIS METHODS

4.1 General principles

The primary objective is to examine whether a two-stage process of shared decision-making and behavioral interviewing improves glycosylated hemoglobin (HbA1c) control and medication adherence among patients who have poorly-controlled diabetes. This is a superiority trial.

The primary outcome is pre to post change in mean HbA1c level from baseline to the follow-up period. There is only one primary outcome, so there will be no multiple testing adjustments.

The primary and secondary outcomes will be evaluated using intention-to-treat principles among all assigned patients. Within the intervention group, patients who choose to speak with a pharmacist may differ from those who do not, and an intention-to-treat analysis in this randomized study ensures unbiased comparisons to the control group.

For all outcomes, statistical significance is defined based on $p < 0.05$ level and using two-sided steps. For continuous data, we will present the results as n and mean (standard deviation). For binary data, we will present the data as n (%). We further describe the analysis of and tests used for each of the outcomes in Section 4.2.

The secondary objective is to develop prediction models and examine their ability to predict response to the study intervention based on baseline patient characteristics, such as sociodemographic, clinical, and medication use characteristics, as well as initial receptiveness to changing health behaviors. We will describe the analysis of this objective further in Section 4.2.

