2.1 Primary objective

Primary Objective:	Outcome Measure:
To examine whether a two-stage process of shared decision-making and behavioral interviewing improves glycosylated hemoglobin (HbA1c) control and medication adherence among patients who have poorly-controlled diabetes.	
Glycosylated hemoglobin (HbA1c):
 
 - Primary outcome: Pre- to post-intervention change in mean HbA1c levels - Mean levels in each study arm in the follow-up period - Proportion of patients in each study arm achieving optimal HbA1c control in the follow-up period 
Medication adherence:
 
 - Continuous proportion of Days Covered (PDC) in each study arm in the follow-up period - Proportion of patients in each study arm achieving optimal adherence (PDC ≥ 0.80) in the follow-up period

Date

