3. PRIMARY AND SECONDARY VARIABLES

3.1 Primary outcome (mean change in glycemetic control):

The primary outcome of interest will be the pre- to post-intervention change in mean HbA1c levels to the end of the 12-month follow-up period. Follow-up will begin from the date of treatment group assignment. The data for this outcome will be based on laboratory information that Horizon Blue Cross Blue Shield of New Jersey receives from over 200 patient-centered medical homes and other population health programs used for quality improvement monitoring. This laboratory information will be used to measure the change in HbA1c levels at the end of follow-up. In specific, the HbA1c result recorded closest to the 12-month end of follow-up as provided in the laboratory data will be used for the primary analysis.

For subjects with missing outcome data, multiple imputation will be used to impute missing follow-up values to calculate the change in HbA1c levels.¹⁰ Of note, all patients by definition for inclusion in the study will have baseline HbA1c values. This imputation approach is used to generate multiple results for missing values based on the underlying distribution of the available data. We will test the robustness of this approach with sensitivity analyses that use alternative methods of handling missing data, including complete case analysis.

This outcome will be analysed formally. We will also explore any potential differences in effectiveness by the pharmacist delivering the intervention.

3.2 Secondary outcome (proportion achieving glycemic control):

The secondary glycemic outcome will include the proportion of patients achieving optimal glycemic control. Optimal glycemic control will be defined as the proportion of patients who achieved an HbA1c result <8.0% in the 12-month follow-up period. This conservative threshold is based on the minimum threshold that nearly all patients should achieve based on guidelines from the American Diabetes Association (ADA) and quality measures used to assess the performance of health plans.^{11,12} In specific, we will use the laboratory information provided to Horizon and will use the HbA1c result recorded closest to the 12-month end of follow-up for the primary analysis.

For subjects with missing outcome data, we will use multiple imputation to impute missing follow-up values to calculate the proportion of patients who achieved this threshold.

This outcome will be analysed formally.

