3.3 Secondary outcome (two medication adherence outcomes):

Medication adherence will be measured using filling patterns in pharmacy claims data for medications that qualified a patient for inclusion in the study.¹³ For each medication, we will create a drug supply diary linking all observed fills after initiation based on dispensing date and days' supply. Different drugs in the same chemically-related therapeutic class (e.g., sulfonylureas) will be considered to be interchangeable. We will allow for up to 180 days of carryover supply. From these supply diaries, we will calculate the proportion of days that patients had medications available to them, or the proportion of days covered (PDC), by dividing the number of days with medication available by the number of days during follow-up.¹⁴ If a patient loses continuous eligibility during the year after the index date, the PDC will be calculated based on the number of days available. If a patient loses continuous eligibility during the year after the index date, they will be censored on that date, and the PDC will be calculated based on the number of days available. In this PDC measurement, if patients had at least one antidiabetic medication available, then they will be considered to be adherent for that day. This definition allows for outcome measurement even when patients switch (e.g., switch from metformin to a sulfonylurea) or intensify therapy (e.g., adding a second oral diabetes medication or injectable medication).

Using this PDC measure, we will observe *1) the mean PDC in each study arm* and *2) the proportion of patients achieving optimal adherence* (defined by ≥ 0.80 PDC) as adherence outcomes in the follow-up period. In a sensitivity analysis of this outcome, medication adherence will be measured by calculating the PDC beginning from the first fill of a medication after assignment until the end of the 12-month follow-up. There will be no missing data for these outcomes, as previously described.

These outcomes will be analysed formally.

3.4 Secondary analyses:

Resource utilization:

As secondary analyses, we will also measure healthcare spending and healthcare resource utilization, including outpatient visits, emergency room visits, and hospitalizations, in the follow-up period in the medical and pharmacy claims data. Healthcare spending will be measured as total allowed amounts in

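### The SAP's reason for no multiplicity adjustment covers only the HbA1c-change test, yet the primary objective also takes in adherence and every outcome is judged at two-sided p<0.05

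*SAP*

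**What the plan says.** SAP 4.1 names a single primary outcome: "The primary outcome is pre to post change in mean HbA1c level from baseline to the follow-up period". It then states "There is only one primary outcome, so there will be no multiple testing adjustments". Shortly afterwards it gives one significance rule for everything: "For all outcomes, statistical significance is defined based on" a two-sided p-value below 0.05.

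The primary objective is wider than the primary outcome. Protocol 2.1 words it as "To examine whether a two-stage process of shared decision-making and behavioral interviewing improves glycosylated hemoglobin (HbA1c) control and medication adherence", and its outcome table lists mean PDC and PDC of at least 0.80 beside the HbA1c measures. SAP 1.1 and 4.1 repeat the same scope.

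SAP Section 3 separates outcomes that are formally analysed from those that are only described. Eight fall in the formal group:

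- 3.1: change in HbA1c
- 3.2: HbA1c <8%
- 3.3: mean PDC, and PDC of at least 0.80 ("These outcomes will be analysed formally")
- 3.4: healthcare spending, office visits, emergency room visits and hospitalisations (the same sentence is repeated)

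Neither document gives a testing order or a gatekeeping rule, or says that p-values for outcomes other than the primary are exploratory.

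**The concern.** A single primary outcome justifies leaving one test unadjusted. It does not settle what may be concluded from the other seven, which are held to the same threshold.

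The gap matters most for the primary objective. Suppose change in HbA1c is not significant, but HbA1c <8%, mean PDC or PDC of at least 0.80 has p<0.05. Under SAP 4.1 that result is statistically significant, and it concerns something the primary objective names. A report could then say the objective was met in part, with no error control behind the statement. The adherence half of the objective has two tests and no rule for combining them.

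**Working it through.** **The plan's own figure.** The documents state no familywise error rate. The nearest stated figure is the sample size for the primary test in Protocol Table 5 (difference 0.5, SD 1.9, two-sided alpha 0.05, power 0.80).

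- n per arm = 2 × (1.960 + 0.842)² × 1.9² / 0.5² ≈ 227 by the normal approximation; the t-test version gives 227.6, so 228, as stated.
- 228 × 1.03 = 234.8; / 0.75 = 313.1; / 0.45 = 695.8, against 696 stated.

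The figure reproduces with the whole 0.05 spent on change in HbA1c and no allowance for other tests.

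**False-positive chance with no true effect.** For k independent tests, the chance of at least one p<0.05 in either direction is 1 − 0.95^k. In the direction of benefit it is 1 − 0.975^k. Whatever the dependence, these cannot exceed 0.05k and 0.025k.

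| Outcomes | k | Either direction | Benefit direction | Upper bounds |
|---|---|---|---|---|
| Change in HbA1c | 1 | 5% | 2.5% | 5%, 2.5% |
| Two PDC outcomes | 2 | 9.8% | 4.9% | 10%, 5% |
| Four HbA1c and adherence outcomes | 4 | 18.5% | 9.6% | 20%, 10% |
| All eight formal outcomes | 8 | 33.7% | 18.3% | 40%, 20% |

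**Allowing for correlation.** The two HbA1c outcomes share one measurement and the two PDC outcomes share another, so independence overstates the risk. The documents give no correlations. The assumptions here are 0.7 between the HbA1c outcomes, 0.8 between the PDC outcomes and 0.2 to 0.5 elsewhere. Simulating correlated normal test statistics gives:

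- four outcomes: about 14 to 15% in either direction, and about 7 to 8% for benefit;
- the two PDC outcomes alone: 7.8% in either direction, 3.9% for benefit.

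For all eight, an assumed common correlation of 0.3 to 0.7 gives 30% down to 19% in either direction, and 15% down to 10% for benefit.

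**The scenario that matters.** This is a non-significant change in HbA1c with a false benefit on at least one of HbA1c <8%, mean PDC and PDC of at least 0.80. If independent: 0.95 × (1 − 0.975³) = 0.95 × 0.0731 = 6.9%. With the assumed correlations it is about 5%.

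**Cost of adjusting the primary as well.** Bonferroni over four tests (0.0125 each) would raise the base size from 227 to 323 per arm, or cut power at 228 per arm to 62%. Over eight (0.00625 each) the figures are 370 and 53%. A procedure that tests change in HbA1c first at 0.05 has no such cost.

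**The case against.** The labels already carry a hierarchy. The Protocol 2.1 table marks change in HbA1c as the primary outcome. Protocol 8.1 and SAP 3.2 and 3.3 call HbA1c <8% and adherence secondary. Spending and utilisation are headed as secondary analyses and are not listed under the primary objective. The as-treated comparison is kept out of the primary analyses (SAP 2.1). Results are to be shown with 95% confidence intervals, and formal analysis may mean only that an outcome is modelled. This is also a pragmatic study with no investigational product.

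Much of this stands. Leaving the primary test unadjusted is correct, and unadjusted secondary outcomes are acceptable when they are called exploratory. The SAP never calls them that: it applies one significance rule to all outcomes. SAP 4.2.1 also places HbA1c <8% and both PDC outcomes after the primary-analyses heading and before the secondary-analyses heading. Adherence has its own sizing at alpha 0.05 and power 0.80 in Protocol Table 6, and a power statement in SAP 1.3, so it was planned as a target for inference.

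A reader might go further and infer that a false claim of benefit is likely. The documents do not support that. Even with no effect on anything, the benefit-direction chance is at most 10% for the four outcomes and at most 20% for all eight. The 34% counts false harm as well as false benefit. It also pools spending and utilisation, for which the plan names no direction of benefit and which cannot show that the primary objective was met. Nor does either document say that the objective will be declared met in part; they simply do not rule it out.

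**Conclusion.** The point holds as a gap in what the SAP allows to be concluded. The change-in-HbA1c test is sound at 0.05. Beyond it, the reason given for making no adjustment does not apply, and the adherence half of the primary objective can be claimed without error control.

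The most relevant size is that for the four HbA1c and adherence outcomes: 18.5% for any false positive and 9.6% for a false benefit under independence, falling to about 14 to 15% and 7 to 8% under correlation. All of these assume no true effect on any outcome, and the correlated figures rest on correlations the documents do not give. Eight is a count of outcomes only; adjusted, subgroup, interaction and as-treated analyses come on top. The four spending and utilisation outcomes appear in the SAP but not in the protocol, although SAP Section 6 records no changes, which is a further reason to state the hierarchy of claims. This is a cheap improvement and not a flaw in the primary analysis.

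**What to change.** Amend SAP 4.1 to say that the confirmatory conclusion rests on change in HbA1c alone, at two-sided 0.05. HbA1c <8%, both PDC outcomes, spending, utilisation, subgroup and as-treated results would then be reported as estimates with 95% confidence intervals and no claim of statistical significance. Limit the blanket significance sentence to match.

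If the sponsor wants a confirmatory adherence claim, prespecify a procedure that opens only when change in HbA1c is significant: a fixed sequence, or Holm across the chosen outcomes. The sponsor should choose the order deliberately. Placing HbA1c <8% ahead of adherence would let a miss there block the one secondary domain that was separately sized.

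SAP 2.2 treats database lock (late March 2018) as still to come, so a change made before then would be prespecified. It needs no patients and leaves the primary test and its sample size unchanged. The price is that an adherence result is not confirmatory unless it is gatekept, and not then if change in HbA1c is not significant.

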4.2 Analysis methods

4.2.1 Primary objective (Effectiveness of intervention):

Baseline characteristics:

We will measure key baseline characteristics in the 12-months prior to randomization in the pharmacy and medical claims data and enrolment files. These characteristics will include sociodemographic characteristics, such as age and sex, which will be measured in the enrolment files. We will also measure baseline clinical characteristics such as the presence of coronary artery disease, chronic obstructive pulmonary disease, asthma, hypertension, hyperlipidemia, congestive heart failure, depression, liver disease, chronic kidney disease, osteoporosis and prior macrovascular complications. These will be measured in medical claims files using ICD-10 codes. We will also measure the type of oral glucose-lowering agent used in the baseline period (e.g., medical class), average PDC at baseline, and whether or not the medication is branded. We will also measure patients' latest copayments for oral glucose-lowering agents in the baseline period. Finally, we will also measure baseline healthcare resource utilization variables as characteristics including the number of days hospitalized and the number of physician office visits.

We will report, in tabular format, the means and frequencies of baseline characteristics prior to assignment separately for patients in the intervention and control groups and compare these values using t-tests, chi-square tests, and their non-parametric analogues, as appropriate. We will provide absolute standardized differences between the two treatment groups.

Primary analyses:

Primary outcome (change in HbA1c): In the primary analysis, the primary outcome, mean change in glycemic control, will be compared using generalized estimating equations with an identity link function (as a continuous variable) and normally distributed errors within the imputed full analysis set, as described above. Data will be presented as the unadjusted absolute difference in the change in HbA1c between the groups along with 95% confidence intervals.

Secondary outcome (proportion achieving glycemic control)

1) *Proportion of patients achieving optimal glycemic control* (defined by HbA1c < 8): This outcome will be compared using generalized estimating equations with a logit link and binary distributed errors. Data will be presented as the unadjusted odds ratio for optimal glycemic control between the groups along with 95% confidence intervals.

Secondary outcomes (medication adherence):

1) *Mean PDC in each study arm:* This outcome will be compared using generalized estimating equations with an identity link function and normally distributed errors. Data will be presented as the unadjusted absolute difference between the groups along with 95% confidence intervals.

2) *Proportion of patients achieving optimal adherence* (defined by ≥ 0.80 PDC): This outcome will be compared using generalized estimating equations with a logit link and binary distributed errors. Data will be presented as the unadjusted odds ratio for optimal adherence between the groups along with 95% confidence intervals.

Secondary analyses:

Healthcare resource utilization and spending: Secondary analyses of healthcare resource utilization will use a similar approach as the primary analysis among the full analysis set, except that we will use log link functions with Poisson errors to describe the count data. Health spending will also be evaluated with variances proportional to the mean (e.g., Poisson-like errors) using log-link functions in generalized estimating equations, which has been found to describe insurer healthcare spending data accurately based on prior research.⁵ Data will be presented as the unadjusted odds ratio along with 95% confidence intervals.

Adjusted analyses: If there are differences in baseline characteristics between study groups that are believed to be confounders (defined by a standardized mean difference of >0.1), we will repeat all of our analyses for the primary and secondary outcomes after adjusting for these covariates in multivariable regression. We will present these as adjusted effect estimates along with 95% confidence intervals.

Interactions: We will also explore any potential differences in effectiveness by the specific pharmacist delivering the intervention by evaluating effect measure modification and using interaction terms within the main model for the primary outcome of change in HbA1c. We will present p-values for interactions.

Subgroups: Subgroup analyses of the primary outcome (change in HbA1c) will also be performed for key subgroups, according to age, sex, depression, and baseline medication adherence levels. These analyses will be performed separately among subgroups of the characteristics and compared between the treatment arms. Data will be presented as unadjusted absolute differences in the change in HbA1c along with 95% confidence intervals.

Sensitivity analyses:

For the glycemic control outcomes, we will also conduct a complete case analysis among patients with complete HbA1c follow-up data. We will also repeat our analyses with longitudinal modeling methods in generalized estimating equations that incorporate any additional HbA1c laboratory values in the 12-month follow-up period, for both the primary outcome of change in HbA1c and secondary outcome of the proportion achieving optimal control.

4.2.2 Secondary objective (Prediction modelling):

Overview

As a secondary aim, we will use predictive analytic approaches to examine whether the clinical outcomes could have been predicted based on patient factors, such as sociodemographic, clinical, medication use and receipt of the pharmacist-delivered telephonic intervention. The goal is also to identify patients who were most likely to respond to this type of intervention. In this aim, we will retrospectively examine whether these characteristics predict glucose control (e.g., HbA1c $<8\%$) and medication adherence (e.g., PDC ≥ 0.80). Specifically, we will evaluate prediction models with respect to their ability to discriminate and explain variation between patients who did and did not meet the glycemic and medication adherence targets during the follow-up period.

Model definitions:

To assess the ability to predict patients who will respond to the intervention, for each outcome (e.g., HbA1c $<8\%$ and PDC ≥ 0.80), we will develop and estimate a series of logistic regression models for patients in both the treatment and control groups, incorporating different patient characteristics

(described in 4.2.1) as predictors. We will model these particular outcomes because these are considered to be clinically meaningful cut-points for achieving optimal control for diabetes and adherence, respectively, and will be meaningful measures for providers, policymakers, and payers alike. For these models, the outcome will be treatment response as defined by each outcome and will include different numbers of predictor variables, in a method similar to previous work.^{16,17} As predictors in these models, we will incorporate patients' baseline demographic, clinical, and resource utilization characteristics.

Model estimation and validation:

For each outcome (e.g., $HbA1c < 8\%$ and $PDC \geq 0.80$), we will first estimate a model that includes only demographic and clinical characteristics. We will then estimate additional models that include these predictors as well as baseline medication adherence. Receipt of the pharmacist intervention will be tested using an interaction term so the logistic regression will provide estimates on all patients and not just those receiving the intervention. We will also repeat the analyses among the subgroup of intervention patients who had at least 1 telephonic encounter with a pharmacist to examine which set of characteristics are most predictive of the response to the intervention. Model estimation will be repeated among relevant patient subgroups (e.g., gender, age) to see if there are any differences in predictive ability.

Models among each of the control and intervention groups will be predicted using both logistic regression and generalized boosting regression, a data mining technique that generates a prediction model through building many regression trees with the potential for many interactions among the predictors.¹⁸ Through these many regression trees, the model can incorporate a number of non-linear associations between the predictors and the outcomes; this approach is considered to be one of the best prediction approaches. Alternative methods of clustering patients who are most likely to respond will also be explored, including machine learning to develop models algorithmically, to partition patients into clusters that have a similar likelihood of experiencing the clinical outcomes.¹⁹

Model accuracy:

To compare the accuracy of the prediction models, we will compare discrimination, the ability of the model to distinguish between patients who do and do not experience the outcome, by the C-statistic. A C-statistic of 1.0 indicates perfect prediction and a value of 0.5 indicates no association.^{8,20} Pseudo R-squares will be used to assess model performance by examining the degree of variation explained by the model, ranging from 0 (no variation explained) to 1.0 (all variation explained)²¹. As secondary analyses, we will also model the change in HbA1c as well as continuous PDC at the end of the follow-up period using linear regression and boosted linear regression, using R-squares to examine predictive ability. To avoid "over optimism" bias associated with evaluating prediction accuracy in the same data used for estimation, we will perform 10-fold cross-validation, which randomly partitions a sample of data into different partitions (leaving 10% of the data out each time) 10 times and averages the validation results over the 10 repetitions.⁸

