To assess the ability to predict patients who will respond to the intervention, for each outcome (e.g., $HbA1c < 8\%$ and $PDC \geq 0.80$), we will develop and estimate a series of regression models for patients in both the treatment and control groups, incorporating different patient characteristics as predictors. We will model these particular outcomes because these are considered to be clinically meaningful cutpoints for achieving optimal control for diabetes and adherence, respectively, and will be meaningful measures for providers, policymakers, and payers alike. For these models, the outcome will be treatment response as defined by HbA1c and PDC and will include different numbers of predictor variables, in a method similar to previous work.^{35,36} As predictors in these models, we will incorporate patients' baseline demographic, clinical, and medication use characteristics and information from the brief screening assessment during the initial pharmacist-delivered telephonic encounter. These baseline demographic, clinical, and medication use characteristics will be measured using Horizon BCBSNJ outpatient pharmaceutical, medical, and laboratory claims files. Some of the models will include only predictors available from administrative claims and not information from patient self-report. We will also assess the correlation between responses to the survey, baseline adherence as measured by pharmacy claims, and response to the intervention.

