1.2 Study design

ENGAGE-DM (ENhancing outcomes through Goal Assessment and Generating Engagement in Diabetes Mellitus) is a pragmatic, prospective, intention-to-treat, randomized controlled trial designed to examine the impact of a novel intervention among patients with T2D that combines behavioral interviewing and shared decision-making delivered by pharmacists over the telephone compared with usual care. After the completion of the trial, we will examine whether a patient's response to the intervention could have been predicted based on their demographics, comorbidities or medication treatment-related factors.

This trial is being conducted among commercially-insured individuals whose medical and prescription benefits are administered by Horizon Blue Cross Blue Shield of New Jersey (Horizon). Horizon is the largest health insurer in New Jersey and administers plans for over 3.8 million beneficiaries.

Following the principles of pragmatic trial design, potentially eligible patients for inclusion in this study were those who: (1) were ≥ 18 years of age, (2) had filled a prescription for 1 or more oral hypoglycemic agents within the prior 12 months, and (3) had evidence of poor glycemic control (A1C $\geq 8\%$) within the previous 6 months, assessed using the most recent HbA1c lab values provided to Horizon Blue Cross Blue Shield. If patients had multiple HbA1c lab values, the latest value was evaluated. An HbA1c threshold of 8% was chosen based on the minimum threshold that nearly all patients should achieve based on guidelines from the American Diabetes Association (ADA); it is also a threshold for major quality measures for health plans. Patients were excluded if, prior to identification, they had fewer than 3 months of continuous enrolment in the health plan, had recently filled insulin (e.g., to exclude patients with type 1 diabetes), or had no available telephone contact information, which would preclude contact for enrolment and delivery of the intervention.

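### The SAP's Aim 2 predictor list names neither baseline HbA1c nor laboratory data, although glycemic response (HbA1c <8%) is the complement of the entry criterion (≥8%)

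*SAP*

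**What the plan says.** **Entry and endpoint.** SAP 1.2 requires the latest HbA1c in the previous six months to be 8% or higher, and gives the reason: "An HbA1c threshold of 8% was chosen based on the minimum threshold that nearly all patients should achieve". SAP 3.2 defines optimal control as "the proportion of patients who achieved an HbA1c result <8.0% in the 12-month follow-up period", using the result closest to month 12. SAP 4.2.2 makes this cut-point one of the two Aim 2 responses: "the outcome will be treatment response as defined by each outcome and will include different numbers of predictor variables". The other is PDC of at least 0.80.

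**Predictors in the SAP.** SAP 4.2.2 points back to 4.2.1 and summarises the inputs as "baseline demographic, clinical, and resource utilization characteristics". SAP 4.2.1 states its sources: "We will measure key baseline characteristics in the 12-months prior to randomization in the pharmacy and medical claims data and enrolment files". It then names age, sex, eleven diagnoses or complications, class of oral agent, baseline PDC, brand status, copayment, hospital days and office visits. The model sequence starts with demographic and clinical characteristics and then adds baseline adherence. No step adds starting HbA1c.

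**Predictors in the protocol.** Protocol 8.1 (Aim 2) draws the baseline predictors from "Horizon BCBSNJ outpatient pharmaceutical, medical, and laboratory claims files". It does not name baseline HbA1c either. SAP section 6 lists no change from the protocol.

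**Availability.** SAP 3.1 says "all patients by definition for inclusion in the study will have baseline HbA1c values", and SAP 2.2 says laboratory values will be sent to the analysts.

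**The concern.** Response is the exact complement of entry, so the fall a patient needs in order to count as a responder is set by where that patient started. A patient at 8.1% needs a fall of just over 0.1 point; a patient at 11% needs more than 3 points. Starting HbA1c is therefore the obvious first predictor of crossing 8%.

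If it is left out, any characteristic that travels with starting level can take up part of its association. Drug class, baseline PDC and prior complications are plausible candidates, though the documents do not say how strongly they are related to HbA1c. Aim 2 is meant to tell payers which patients respond to pharmacist engagement. A marker of a low start could then be read as a marker of benefit.

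The exposure is greatest in the models fitted separately by arm and in the model restricted to intervention patients with at least one pharmacist call. The latter is meant to show which characteristics predict response, but it has no control arm against which to separate starting level from response.

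**Working it through.** No figure in the documents bears directly on this point, so there is none to reproduce. The check is a large-sample simulation, and its inputs are mostly assumptions.

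**Inputs**
- Follow-up SD 1.9: the SAP 1.3 planning value.
- Uniform treatment effect of 0.5 point: the SAP 1.3 target difference.
- Assumed: baseline HbA1c = 8 + exponential excess with mean 1.4, so mean 9.4 and SD 1.4.
- Assumed: usual-care follow-up mean 8.6.
- Assumed: baseline-to-follow-up correlation ρ of 0.2 to 0.6.

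**Model.** Follow-up = 8.6 + ρ × 1.9 × z + error, where z = (baseline − 9.4)/1.4 and the error SD is 1.9 × √(1 − ρ²). A responder has follow-up below 8.

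**Step 1: how much baseline HbA1c predicts, under usual care**

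| ρ | C-statistic, baseline HbA1c alone | Responders, start <8.5% | Responders, start ≥10% |
|---|---|---|---|
| 0.2 | 0.58 | 44% | 27% |
| 0.3 | 0.61 | 47% | 23% |
| 0.4 | 0.65 | 51% | 19% |
| 0.5 | 0.69 | 55% | 15% |
| 0.6 | 0.73 | 59% | 11% |

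Varying the baseline mean from 9.0 to 10.0 and its SD from 1.0 to 1.5 gives similar C-statistics: 0.58 to 0.59 at ρ = 0.2 and 0.69 to 0.70 at ρ = 0.5.

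**Step 2: what a pure proxy picks up.** Take a predictor correlated 0.3 with baseline HbA1c and with no effect of its own. With baseline HbA1c omitted, its log odds ratio is about −0.09 per SD at ρ = 0.2, and −0.13 to −0.22 for ρ = 0.3 to 0.6. With baseline HbA1c in the model it is about 0 (at most 0.005 in size). Used alone, the proxy has a C-statistic of about 0.53 to 0.56. Across proxy correlations of 0.1 to 0.4 and ρ up to 0.7, the range is 0.51 to 0.60.

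**Step 3: the pooled interaction test.** Lower every treated patient's follow-up HbA1c by 0.5.

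| ρ | Odds ratio, start <8.5% | Odds ratio, start ≥10% |
|---|---|---|
| 0.3 | 1.55 | 1.56 |
| 0.4 | 1.58 | 1.59 |
| 0.5 | 1.63 | 1.65 |
| 0.6 | 1.71 | 1.74 |

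On the logit scale a uniform effect looks uniform. In the wider grid (ρ = 0.3 to 0.7, effects of 0.15 and 0.5), the proxy-by-treatment coefficient never exceeds 0.04 per SD in size. On the absolute scale the same uniform effect does differ: about 11 to 12 percentage points near the cut, against 6.5 to 9 at 10% or above (ρ = 0.3 to 0.6).

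**Step 4: the HbA1c-change models.** The correlation of change with baseline is (ρ × SD_F − SD_0)/√(SD_F² + SD_0² − 2ρ × SD_F × SD_0), where SD_F and SD_0 are the follow-up and baseline SDs.
- ρ = 0.3: (0.57 − 1.40)/√(3.61 + 1.96 − 1.596) = −0.83/1.99 = −0.42.
- ρ = 0.6: (1.14 − 1.40)/√(3.61 + 1.96 − 3.192) = −0.26/1.54 = −0.17.

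High starters fall further through regression to the mean. A marker of a high start therefore looks unfavourable in the threshold model and favourable in the change model. This reversal needs ρ × SD_F < SD_0. With a baseline SD of 1.0 it has nearly gone at ρ = 0.5 (0.95 against 1.0).

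**The case against.** **The lists are open.** SAP 4.2.1 introduces its items as examples, clinical characteristics could include HbA1c, Protocol 8.1 names laboratory files, and the SAP declares no departure from the protocol. This stands in part. A reader might infer that baseline HbA1c is excluded; it is only unnamed. But the SAP's source list is specific and drops the laboratory file, and nothing in the model sequence brings the value in. An analyst who follows it literally would leave HbA1c out.

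**Proxies are weak.** A reader might infer that the models will find mainly proxies. That is not shown: a pure proxy reaches a C-statistic of only about 0.51 to 0.60, and its size depends on correlations the documents do not give.

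**The planned interaction test is robust.** A reader might also infer that a constant effect will appear as differential response. On the scale of the pooled logistic interaction in SAP 4.2.2 it does not (step 3). The contrast appears only if benefit is expressed in percentage points.

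**The C-statistics are not biased.** A cross-validated C-statistic describes the model actually fitted. Omitting a strong predictor makes for a weaker model; it does not make the statistic understated.

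**Scope is limited.** For PDC of at least 0.80 the baseline analogue, average PDC, is listed and entered, so that half of Aim 2 is not at issue. The secondary models of HbA1c change offer a measure free of the threshold, but without baseline HbA1c they carry the problem in step 4.

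**Conclusion.** The point holds in limited form. The SAP names neither baseline HbA1c nor a laboratory source for its Aim 2 predictors, although the glycemic response is defined by the same cut as entry and the value is held for every patient. The difference in sources from Protocol 8.1 is undeclared.

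The consequence falls on main effects, on the separate models by arm, and on the model confined to patients who spoke with a pharmacist. These discriminate less well than they could and may credit characteristics that only mark starting level. The direction rests on baseline and follow-up HbA1c being positively correlated, which is hard to doubt. The size rests on an assumed baseline distribution and assumed correlations, so the figures above are illustrations and not predictions for this trial.

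The randomized comparison on the primary outcome is untouched. What is at risk is the advice on whom to target, which is the purpose of Aim 2, so the correction is worth making before the models are fitted.

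**What to change.** - Add the qualifying HbA1c, as a continuous variable, to the baseline characteristics in SAP 4.2.1, and add the laboratory file to the stated sources. This restores agreement with Protocol 8.1; otherwise the difference should be declared in SAP section 6.
- Enter it from the first model onward in every Aim 2 model of HbA1c <8% and of HbA1c change, including the arm-specific and intervention-only models. Include its interaction with the intervention in the pooled model.
- Report the gain in C-statistic or R-square from the other predictors over a model with baseline HbA1c alone.
- Optional: a non-linear term, and the age of the laboratory value at assignment.

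The cost is a few lines of SAP text and one variable already held. No new data are needed. The increment reported for the other predictors may be smaller, but it will be easier to interpret.
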